6.4 Stopping Rules

There are no stopping rules

7.0 DRUG INFORMATION

7.1 Levothyroxine

- Other names for the drug(s): Tirosint, Synthroid
- Classification - type of agent: Thyroid hormone
- Mode of action: Synthetic levothyroxine is identical to that produced naturally in the human thyroid gland.
- Storage and stability: room temperature
- Protocol dose: Starting dose will be 1.5-1.8 mcg per kg, using the patient's actual weight. Dose will be rounded to the nearest available incremental dose of the randomized formulation. Dose will be adjusted to next higher or next lower dose during follow up visits based on TSH values. Doses can be initiated or adjusted by single or combination of preparations listed below. Note: if dose requires use of 12.5 mcg or 13 mcg, exact dose will be determined based on the brand to which the subject was randomized. This is due to gel capsules only available in 13 mcg while tablets can only be split to 12.5 mcg.
- Route of administration for this study: oral
- Incompatibilities: Must be taken on an empty stomach. Must wait at least 1 hour before taking food/water/other medications or vitamins
- Availability: commercially available, both formulations will be encapsulated in a fashion to allow double blinding. The available strengths above (including 12.5 mcg split from 25 mcg Synthroid) will be encapsulated by an outside compounding pharmacy. The medication will be shipped directly to the Aston research pharmacy (8th floor) that will dispense all medication and will not be blinded. The Aston pharmacy will be given the randomization code for the patient by the study statistician, [name]. The pharmacy will dispense medication according to the randomization.
- Side effects: Adverse Reactions associated with levothyroxine therapy are symptoms of hyperthyroidism due to therapeutic over-dosage.
- Nursing implications: none

STU022015-044, [name], Form A, Mod_14, 07-29-19

CONFIDENTIAL

This material is the property of the [UTSW Simmons Cancer Center](#). Do not disclose or use except as authorized in writing by the study sponsor.

Template Updated: 12/2012; 9/2013; 8/2014; 4/2015; 10/2015; 11/2016, 12/2018

- Pharmacokinetics – from package inserts of Tirosint and Synthroid which is identical except for absorption.
 - Absorption:
 - Absorption of orally administered T₄ from the gastrointestinal (GI) tract ranges from 40% to 80%. The majority of the levothyroxine dose is absorbed from the jejunum and upper ileum. The relative bioavailability of TIROSINT capsules compared to another marketed levothyroxine sodium tablet is approximately 103%. **The relative bioavailability of SYNTHROID tablets, compared to an equal nominal dose of oral levothyroxine sodium solution, is approximately 93%.** T₄ absorption is increased by fasting, and decreased in malabsorption syndromes and by certain foods such as soybeans. Dietary fiber decreases the bioavailability of T₄. Absorption may also decrease with age. In addition, many drugs and foods affect T₄ absorption.
 - Distribution
 - Circulating thyroid hormones are greater than 99% bound to plasma proteins, including thyroxine-binding globulin (TBG), thyroxine-binding prealbumin (TBPA), and thyroxine-binding albumin (TBA), whose capacities and affinities vary for each hormone. The higher affinity of both TBG and TBPA for T₄ partially explains the higher serum levels, slower metabolic clearance, and longer half-life of T₄ compared to T₃. Protein-bound thyroid hormones exist in reverse equilibrium with small amounts of free hormone. Only unbound hormone is metabolically active. Many drugs and physiologic conditions affect the binding of thyroid hormones to serum proteins
 - Metabolism
 - T₄ is slowly eliminated. The major pathway of thyroid hormone metabolism is through sequential deiodination. Approximately 80% of circulating T₃ is derived from peripheral T₄ by monodeiodination. The liver is the major site of degradation for both T₄ and T₃, with T₄ deiodination also occurring at a number of additional sites, including the kidney and other tissues. Approximately 80% of the daily dose of T₄ is deiodinated to yield equal amounts of T₃ and reverse T₃ (r T₃). T₃ and r T₃ are further deiodinated to diiodothyronine. Thyroid hormones are also metabolized via conjugation with glucuronides and sulfates and excreted directly into the bile and gut where they undergo enterohepatic recirculation.
 - Elimination
 - Thyroid hormones are primarily eliminated by the kidneys. A portion of the conjugated hormone reaches the colon unchanged and is eliminated in the feces. Approximately 20% of T₄ is eliminated in the stool. Urinary excretion of T₄ decreases with age.

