2.2 Secondary Objectives

- 2.2.1 To quantify the mean number of dose adjustments, and compare the two study agent group outcomes
- 2.2.2 To assess and compare quality of life differences between study groups using scores on QoL-Thyroid and ThyTSQ surveys

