7.1.1 Return and Retention of Study Drug

The remaining drugs will be destroyed according to the UT Southwestern pharmacy policy.

- #### 7.1.2 Subject's compliance with the study agents will be assessed at every clinical appointment. A pill count will be inventoried by the practitioner and recorded in the patient's electronic medical record.

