8.0 STATISTICAL CONSIDERATIONS

8.1 Study Design/Study Endpoints

This is a double blinded, randomized, single center study. The study will end at the 18 week post-surgical follow up appointment.

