9.5 Data Management and Monitoring/Auditing

Trial monitoring will be conducted by no less than annually and refers to a regular interval review of trial related activity and documentation performed by the study team, which includes but is not limited to accuracy of case report forms, protocol compliance, timeliness and accuracy of Velos entries and AE/SAE management and reporting. Documentation of trial monitoring will be maintained along with other protocol related documents and will be reviewed during internal audit.

Toxicity and dose escalation reviews will be performed by the primary investigator, [name] at each follow up visit. These reviews will be documented in the visit note and electronic medical record.

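### The 12.5 versus 13 mcg step identifies the arm, and the plan does not say that this figure is kept from the investigator who titrates

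*Combined protocol and SAP*

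**What the plan says.** Section 8.1 states the design: "This is a double blinded, randomized, single center study". The blinded roles are not listed. Section 7.1 says that both formulations are encapsulated so that they can be blinded, and that the research pharmacy is not blinded. The pharmacy receives the code from the study statistician and dispenses by it.

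The same section has a note on the smallest strength. If a dose needs 12.5 or 13 mcg, the "exact dose will be determined based on the brand to which the subject was randomized". The reason given is "gel capsules only available in 13 mcg while tablets can only be split to 12.5 mcg". Section 7.1 also provides for the 12.5 mcg half-tablet to be encapsulated and allows starting and adjusted doses to be built from combinations, so this strength is a planned part of dosing. Titration goes to the adjacent dose according to TSH.

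Section 9.5 gives the toxicity and dose escalation reviews at each follow-up visit to the primary investigator and adds: "These reviews will be documented in the visit note and electronic medical record". Section 4.2 places the adjustments at weeks 6 and 12. The first secondary objective (section 2.2) is "To quantify the mean number of dose adjustments" and to compare the arms on it.

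**The concern.** Encapsulation masks what the product looks like. It does not mask a number. If the order, label, visit note or medical record shows a dose built with 13 mcg, the patient is on gel capsules; if it shows one built with 12.5 mcg, the patient is on tablets. The person who reviews and adjusts the dose has to know what the patient is currently taking in order to move to the adjacent dose, and so is the person most likely to meet that figure.

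This matters because the titration decision is itself an outcome. The background (section 1.1) states the hypothesis that the gel capsule will need fewer dose adjustments, and section 2.2 counts those adjustments. A titrator who knows the arm could, without intending to, be readier to adjust in one arm than in the other. Adverse event attribution is open to the same influence, as are the questionnaires if patients see the exact strength.

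**Working it through.** **1. Does the figure identify the arm?** From section 7.1:

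| Strength | Tablet arm | Gel capsule arm |
|---|---|---|
| 12.5 mcg | yes (half of a 25 mcg tablet) | not available |
| 13 mcg | not available | yes |

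The mapping is one-to-one. The difference is small as a quantity: 13/12.5 − 1 = 4.0% for the strength alone, and 113/112.5 − 1 = 0.44% when added to, say, 100 mcg. As a label it fully identifies the arm.

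**2. Do the stated safeguards cover it?** Two are described, both in section 7.1: over-encapsulation (hides appearance) and an unblinded dispensing pharmacy (holds the code). Neither says in which form the dose is ordered, labelled or recorded. Nothing assigns the brand-specific rule to a named role, and nothing withholds the exact mcg from the investigator.

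**3. Is there a route to the titrator?** Section 7.1 (move to the adjacent dose) and section 9.5 (the primary investigator reviews doses at each follow-up visit and documents the review) together put the current dose in front of the investigator in some form. The plan does not say whether that form is the exact mcg or a neutral level.

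**4. How many patients?** The only stated figure is the sample size in section 8.2: 10 + 10 = 20 completers. There is no power calculation to reproduce. The share q who ever use this step is not given, and the list of strengths to which section 7.1 refers is not in the text available for review, so q is an assumption. With patients taken as independent, the expected number is 20q and the chance of at least one is 1 − (1 − q)^20:

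| Assumed q | Expected of 20 | P(at least one) |
|---|---|---|
| 2% | 0.4 | 33% |
| 5% | 1 | 64% |
| 10% | 2 | 88% |
| 20% | 4 | 99% |

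**5. What could one influenced decision do?** With adjustments at weeks 6 and 12, each patient contributes 0, 1 or 2. With 10 per arm, one extra or withheld adjustment moves an arm mean by 1/10 = 0.1. If it also moves one patient into or out of the TSH range at a visit, that arm's proportion on target shifts by 1/10 = 10 percentage points.

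**The case against.** The best defence is that the note in 7.1 already implies masking. It names the step jointly, as 12.5 or 13 mcg, and makes the exact figure depend on the brand. A blinded investigator could not apply that rule; the pharmacy, which holds the code, could. This is a fair reading, and it may be what was intended. It does not remove the point, because no sentence says so and site staff could equally write the exact figure in good faith.

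Other limits also stand. The primary outcome is laboratory TSH against a fixed range, titration follows TSH at two scheduled visits, and the study is descriptive and unpowered, so the room for bias is limited.

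A reader might infer four stronger things that the documents do not support:

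- That section 9.5 orders the exact mcg to be recorded. It says only that the reviews are documented, not in what form the dose appears.
- That every dose reveals the arm, because section 7.1 says: "Dose will be rounded to the nearest available incremental dose of the randomized formulation". That would follow only if other strengths differed between brands, and the documents state no other difference.
- That the pill count reveals the arm. It is a compliance count of over-encapsulated product and does not show 12.5 against 13.
- That the blind is already lost for these patients. It is lost only if the exact figure is disclosed, and this is not established.

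**Conclusion.** The point holds as an unprotected route. A stated dose rule produces an arm-identifying number, the investigator who titrates works from the current dose, and the plan contains no step that keeps the one from the other. It applies only to patients whose dose uses the 12.5/13 mcg step. Their number cannot be derived from the documents; 0.4 to 4 of 20 is the expected range under an assumed share of 2% to 20%, and it is an upper limit on actual unblinding because it supposes that the exact figure is seen.

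The TSH measurement is not at risk. The exposure is in titration decisions, the count of dose adjustments, adverse event attribution and, if patients see the strength, the questionnaires. The pilot status lowers the stakes but does not remove them, since section 8.3 still plans between-group estimates and applies a 0.05 threshold, and a feasibility study is a good place to establish that the blind works. This is a change that should be made because it is cheap; it does not call the design into question.

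**What to change.** Add to section 7.1:

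- Orders, labels, visit notes, the medical record and CRFs carry one common nominal dose level for both arms, with this step written as 12.5/13.
- The already unblinded research pharmacy converts the investigator's nominal order to the brand-specific strength by a fixed one-to-one table. It has no discretion over dose selection. This matters because the 1.5-1.8 mcg/kg starting range may admit more than one strength, and that choice should not pass to someone who knows the arm.
- The exact mcg is kept in the pharmacy log, is available for emergency unblinding, and is merged with the trial data after database lock.
- The blinded roles are named.

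The cost is a few sentences, an order and label template, and a conversion log at the pharmacy. The downside is that, until unblinding, the medical record shows the nominal level and not the 0.5 mcg difference (13 − 12.5). No patient's dose and no sample size changes.

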7.1.1 Return and Retention of Study Drug

The remaining drugs will be destroyed according to the UT Southwestern pharmacy policy.

- #### 7.1.2 Subject's compliance with the study agents will be assessed at every clinical appointment. A pill count will be inventoried by the practitioner and recorded in the patient's electronic medical record.

8.0 STATISTICAL CONSIDERATIONS

8.1 Study Design/Study Endpoints

This is a double blinded, randomized, single center study. The study will end at the 18 week post-surgical follow up appointment.

8.2 Sample Size and Accrual

As this is a feasibility study it will only include 20 total, study-completed participants. Each arm of the study will include 10 patients. Descriptive statistics are of primary interest as this study is not powered to formally test a statistical hypothesis.

8.3 Data Analyses Plans

Continuous variables will be summarized with mean and standard deviation; medians and ranges will be reported for skewed variables. We will construct 95% confidence intervals will be used to estimate liquid gel capsule treatment and tablet treatment responses at each study visit and to estimate differences between groups or visits within groups. This study has repeated measurements and these longitudinal data will be evaluated using a mixed linear model approach for repeated measures. Due to the pilot nature of study any hypothesis testing will be interpreted cautiously. The primary analysis data set will be the intention-to-treat analysis data set consisting of all randomized subjects who have at least one post-randomization study visit. All available data, including cases with missing data, will be included in the statistical analysis. Categorical variables, including any adverse events, will be summarized in detail with descriptive statistics. P values of < 0.05 will be considered statistically significant.

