2.0 STUDY OBJECTIVES

2.1 Primary Objectives

2.1.1 The aim of this investigation is to compare the use of levothyroxine in liquid gel capsules to tablet form for TSH suppression (target 0.1-0.5 MIU/L) following thyroidectomy for presumed stage I/II differentiated thyroid cancer. This will be

STU022015-044, [name], Form A, Mod_14, 07-29-19

CONFIDENTIAL

This material is the property of the [UTSW Simmons Cancer Center](#). Do not disclose or use except as authorized in writing by the study sponsor.

Template Updated: 12/2012; 9/2013; 8/2014; 4/2015; 10/2015; 11/2016, 12/2018

achieved by evaluating the number of patients in each group at the predefined target TSH range at each time interval (6, 12, and 18 weeks (+/- 1 week for each interval) postoperatively). Descriptive statistics are of primary interest as this feasibility study is not powered to formally test a statistical hypothesis.

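### Does the closing P<0.05 rule in section 8.3 undercut the descriptive, unpowered purpose of the pilot?

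*Combined protocol and SAP*

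**What the plan says.** Section 2.1.1 makes the primary measure the number of patients in each arm within the TSH target, counted "at each time interval (6, 12, and 18 weeks" after surgery, and adds: "Descriptive statistics are of primary interest as this feasibility study is not powered to formally test a statistical hypothesis". Section 8.2 sets 20 completers, 10 per arm, and repeats the point: "Descriptive statistics are of primary interest as this study is not powered to formally test a statistical hypothesis". Section 2.2 adds between-arm comparisons of dose adjustments ("To quantify the mean number of dose adjustments, and compare the two study agent group outcomes") and of the QoL-Thyroid and ThyTSQ scores.

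Section 8.3 plans summary statistics, a mixed linear model for the repeated measures, and 95% confidence intervals for the responses in each arm and "to estimate differences between groups or visits within groups". It then says: "Due to the pilot nature of study any hypothesis testing will be interpreted cautiously". On categorical data it says: "Categorical variables, including any adverse events, will be summarized in detail with descriptive statistics". The last sentence of the section is: "P values of < 0.05 will be considered statistically significant".

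**The concern.** A plan that twice disclaims formal testing finishes with a significance threshold that has no stated limit. The request for caution governs tone. It does not say which P values may be called significant or what may be concluded from them. Read literally, a report could call a week-12 difference or a ThyTSQ difference statistically significant and still comply with the plan.

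At stake is the wording of the pilot's conclusions. A chance finding in 20 patients could be presented as an established difference between formulations. Conversely, P above 0.05 with 10 per arm could be presented as evidence that the formulations are alike.

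**Working it through.** **1. Is there a contradiction?** There is no stated power to reproduce, because 8.2 gives no effect size, SD, rate or power. The check is therefore mainly one of text.

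- Sections 2.1.1 and 8.2 rank description first. A ranking leaves room for secondary tests, and 8.3 expressly foresees that some may be done.
- Lack of power concerns missed differences. It does not change the false-positive rate of a single valid 5% test.
- The closing sentence of 8.3 defines a term. It orders no test, and no conclusion, go/no-go decision or later trial is tied to it.
- The primary measure is a count in range at each visit, which is categorical. Section 8.3 assigns categorical variables to descriptive summary, so on its plain reading no visit-level test of that count is planned.

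**2. How often could the label arise by chance?** The plan names no such tests, so the following is assumed: 10 v 10, two-sided 0.05, no true difference, one test per visit (three) and one per secondary outcome (dose adjustments, QoL-Thyroid, ThyTSQ), all independent. Let *a* be the exact rejection rate at one visit, found by enumerating all pairs of counts.

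| True in-range rate | *a*, Fisher | *a*, chi-square (uncorrected) | Any of 3 visits, 1−(1−*a*)³: Fisher / chi-square | All 6, 1−(1−*a*)³×0.95³: Fisher / chi-square |
|---|---|---|---|---|
| 0.2 | 0.0076 | 0.0299 | 0.022 / 0.087 | 0.162 / 0.217 |
| 0.4 | 0.0126 | 0.0403 | 0.037 / 0.116 | 0.175 / 0.242 |
| 0.6 | 0.0126 | 0.0403 | 0.037 / 0.116 | 0.175 / 0.242 |

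Three secondary tests alone: 1−0.95³ = 0.143. Six tests, each of exactly 5% size: 1−0.95⁶ = 0.265. If the six outcomes share a correlation of 0.6, simulation lowers the six-test figures to 13-14% (Fisher for the visits), 18-19% (chi-square) and 19% (all six t-tests).

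With Fisher's test the three visits together stay below 5%. The larger figures come from counting several outcomes. They measure multiplicity, which a descriptive pilot need not control, so they say nothing about whether the closing sentence is out of place.

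**3. Would different wording limit what can be claimed?** Suppose 3/10 v 8/10 are in range.

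- Fisher: P = 0.070.
- Chi-square: pooled rate 11/20 = 0.55; z = 0.5/√(0.55×0.45×0.2) = 0.5/0.2225 = 2.25; P = 0.025.
- Wald 95% interval for the difference: SE = √(0.3×0.7/10 + 0.8×0.2/10) = √0.037 = 0.192; 0.50 ± 1.96×0.192 = 0.12 to 0.88.
- Newcombe 95% interval: 0.07 to 0.74.

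Both intervals exclude zero. If P values were declared nominal and inference moved to the intervals, a report could make the same claim from the interval. The split between Fisher and chi-square shows only that no test is named, which is a separate matter that rewording the threshold would not settle.

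**The case for a change.** The strongest case for a change is that the closing sentence is the only operative decision rule in 8.3 and is worded as a commitment, whereas the caution is only an attitude. The summary of amendments shows that the sponsor added the disclaimer to 2.1.1 on purpose, to stress the pilot character, so a leftover threshold works against a stated intention. Replacing it would take one sentence, touch no data or analysis, and discourage misreading in both directions.

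Part of this stands. The sentence is unrestricted, it fits poorly with its surroundings, and describing P values as nominal would be tidier. What does not stand is that the rule decides what the report may conclude. The request for caution applies to any hypothesis test, so it reaches every visit and every secondary outcome. Two separate disclaimers of power tell the reader how little weight a P value carries here, in either direction. Replacement wording would largely repeat that message.

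**Conclusion.** No change to the plan follows, because none would bring a gain. The closing sentence is a slightly awkward stock phrase in a plan that otherwise makes its descriptive aim plain. It does not contradict 2.1.1 or 8.2, and no stated figure is wrong. Removing or rewording it would leave every estimate, interval, model and decision as it is. An analyst who follows 8.3 as written, caution and disclaimers included, would report estimates with 95% confidence intervals and treat any P value as exploratory.

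The 16-27% chance of at least one nominal P<0.05 depends on six independent tests that the plan does not specify, with true in-range rates of 20-60%, and falls to 13-19% at a correlation of 0.6. It should not be used to judge this sentence. The conclusion assumes that the report carries the plan's own disclaimers alongside any P value.

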9.0 STUDY MANAGEMENT

9.1 Conflict of Interest

Any investigator who has a conflict of interest with this study (patent ownership, royalties, or financial gain greater than the minimum allowable by their institution, etc.) must have the conflict reviewed by the UTSW COI Committee and IRB according to UTSW Policy on Conflicts of Interest. All investigators will follow the University conflict of interest policy.

